## Scenario summary

research topic	Application of Single-Port Robot-Assisted Breast-Conserving Surgery via Axillary Approach for Breast Cancer.
Main purpose of the study	
1. To evaluate the efficacy of single-port robots in breast cancer breast conserving surgery. Including differences in operative time and intraoperative number of lymph nodes detected.
 
2. To evaluate surgical safety: the incidence of surgical transfer and the incidence of postoperative complications.

Secondary purpose of the study	Pain and cosmetic scores of patients after breast conserving surgery under a single port robotic approach.
research design	
 Randomized controlled trial
 
 non-randomized controlled study
 
 Single-arm study
 
 Other
 
 Single-center study    multicenter study
 
Whether blind:  yes  no

subject investigated	Patients undergoing breast-conserving surgery for breast cancer.
intervention study	Single-port Robot-assisted breast-conserving surgery for breast cancer.
endpoint criteria	Success rate of breast conservation surgery under single-port robotic approach
sample capacity	Total number of cases: 100; 20 in the test group; 80 in the control group

statistical analysis	Double data entry was carried out using Excel 2010, and data analysis was performed with SPSS 25.0. The normality of continuous variables and homogeneity of variance were examined by Kolmogorov-Smirnov test and analysis of variance test respectively. For continuous variables that conformed to normal distribution and had homogeneity of variance, the independent-samples t-test was adopted. For continuous variables that did not conform to normal distribution, the Mann Whitney U test was used. For categorical variables and count data, Fisher's exact test and Pearson chi square test were employed.
Study cycle	November 2024-December 2025

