## 1. Research Background

Breast cancer is the second most prevalent female malignancy in China[1]. At present, the most important treatment for breast cancer is still surgical treatment[2-5]. Surgical treatment is inevitable in many cases, and with traditional surgery, it does leave a permanent scar on the chest[6]. Patients with high requirements for breast and breast aesthetic requirements are troubled by this. Studies show that young women of Asian descent (<50 years old) have more dense breasts than white women in the US[7]. So, it is more likely to the scars happen, and the scar repair after breast surgery is also more slow[8,9]. Therefore, minimally invasive breast surgery is necessary for Chinese women. Clinically, breast surgeons carry out different minimally invasive surgical methods and use different surgical approaches (such as axillary approaches) to achieve scar-free and attractive breast cancer surgery.[10,11]

The minimally invasive surgical approach enables better wound healing and less postoperative pain with the same tumor removal effect as open surgery[12]. Robotics is one of the widely used minimally invasive surgery in breast surgery, compared with open surgery, this minimally invasive technique reduces the occurrence of postoperative complications, enhances the protection of limb function, and meets the needs of patients for beauty. The study data showed that the postoperative complication rate of traditional open surgery was 7%, while the complication rate after robotic surgery was only 3.9%[13-15]. At the same time, in addition to the advantages of minimally invasive technology, robotics has its unique characteristics[16-18]. The application of robot technology makes breast surgery realize remote, digital and intelligent. Compared with the endoscopic surgery system, the robot system has a three-dimensional high-definition visual field magnified tens of times, so that the surgeon can have a clearer surgical vision, improve the surgical resolution, and increase the control of the operation. Moreover, the robots rotating wrist surgical instrument arm can rotate for 540°, enabling intuitive movement for a

more flexible and delicate operation[19]. For breast surgery with a narrow surgical area, the application of robotics is particularly important.

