In 2017, robotics was first applied in breast surgery by Toesca et al[20]Since then, the application of robots in breast surgery has been further developed to form robotic prosthetic breast reconstruction and nipple-sparing mastectomy[21-23]. Compared with traditional open breast surgery, robotic breast surgery can retain normal tissue to the maximum extent, and achieve the advantages of small blood loss, less postoperative complications, postoperative symmetry, beauty and feel under the premise of complete tumor removal. However, in the clinical application process, due to the limited breast surgery area, the operation of the traditional multi-arm robot in the narrow surgery area is greatly limited, and there is the phenomenon of operating instruments and mechanical arm collision, which will lead to the failure of the advantages of the robot in breast surgery. The emergence of Single-port robot(SPr) effectively overcomes the disadvantages of multi-arm robot, not only continues the advantages of multi-arm robot surgical system, but also has advantages in minimally invasive, convenience, universality, flexibility, multi-directional operation. It is especially suitable for separation, suture, knot and other operations in a narrow space. Breast-conserving surgery has become one of the standard treatments for breast cancer due to the improved postoperative cosmetic effect, quality of life and acceptable postoperative tumor safety of breast cancer patients[24-28]. In 2024, Liao Ning, a Chinese scholar, gave an oral report on robot-assisted breast cancer breast conservation surgery at the 43rd ESSO. Considering both the completeness of lesion resection and the aesthetic integrity of breast preservation, the surgical approach of SPr approach through axillary incision is more advantageous than that of other approaches[27]。

In recent years, the domestic single-port robot surgical system has developed rapidly and its functions are increasingly perfect. The domestic Jingfeng ®SP1000 single-port robot surgical system will be used in our hospital. The public information

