### 3.2 Technical route

### 3.3 Study population

#### 3.3.1 Inclusion criteria

- 1) The patient himself has very high requirements for beauty, and requires no scar on the chest;
- 2) No chest surgery and radiotherapy.
- 3) No contraindications to surgery and anesthesia.
- 4) Clinical I, stage of early breast cancer and the breast has an appropriate volume, can maintain a good breast shape after surgery.
- 5) Patients in the clinical period who meet the standard of breast conservation

surgery after preoperative treatment.

6) Age: 18 and 65 years old.

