### 3.5 Interventions

**(1) SPr-breast conserving surgery group: using single port robot.**

**(2) Tradition-breast conserving surgery group: breast surgery was**

completed with traditional surgery.

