### 5.1 Adverse events

#### 5.1.1 Definition

(1) Intraoperative and postoperative bleeding and hematoma: the phenomenon of blood vessel rupture at the surgical site and blood outflow outside the blood vessels. After breast preservation surgery for breast cancer, bleeding may be caused by incomplete intraoperative hemostasis, or shedding of postoperative vascular ligation line, abnormal coagulation function, and increased local vascular pressure. The hematoma is a mass-like structure formed by blood accumulation in the local tissue of the operation. It is a consequence manifestation after bleeding. With the continuous accumulation of blood, the formation of hematoma area with a certain boundary, which produces pressure on the surrounding tissue.

(2) Breast flap necrosis: In breast cancer, the skin and subcutaneous tissue flap with blood supply is cut from the supply area (such as the skin tissue around the breast) to cover the surgical wound or reconstruction of partial breast structures. Breast flap necrosis refers to the situation of this part of the flap due to insufficient blood supply, infection and other factors, resulting in tissue cell death. The flap color will gradually become black and harden, lose elasticity and luster, and eventually may appear dry necrosis (such as leather-like changes) or wet necrosis (with exudation, suppuration, etc.).

(3) Necrosis of nipple areola complex: nipple areola complex includes nipple and

areola. The necrosis of nipple areola complex refers to the necrosis of nipple and (or) areola tissue due to the destruction of blood transport (such as cutting off the main blood vessels), local tension, infection and other factors. The nipple areola will appear color change (such as from pink to dark black), sensory loss, the later stage may fall off the tissue and other phenomena.

(4) Subcutaneous emphysema: a pathological phenomenon in which gas enters and accumulates in the subcutaneous tissue space after breast-conserving surgery. Under normal circumstances, there is no gas in the subcutaneous tissue. When the gas (mainly air) enters the subskin through the surgical wound or the damaged area of the surrounding tissue, and forms a certain area of emphysema, subcutaneous emphysema appears.

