(5) Infection: the pathological process of bacteria, fungi, viruses and other invade the incision site, and grow and reproduce in it, causing local inflammatory reaction and (or) systemic reaction. After breast conserving surgery in breast cancer, the skin and tissue integrity. When the sterile environment of the operating room is not up to standard, the surgical instruments and dressings are not thoroughly disinfected, the concept of aseptic is not strong during the operation, the patients immunity is low (such as diabetes, malnutrition, etc.), or the postoperative incision care is improper (such as not changing the dressing in time, wound exposure to contamination, etc.).

(6) Envelar spasm: the process of contraction, thickening and hardening of the fiber capsule around the breast implant. This coating was supposed to be soft and elastic to accommodate the implant and maintain the natural shape and softness of the breast. But during the capsular contracture, it is gradually tightened, squeezing the implant.

(7) Postoperative shoulder pain: shoulder-centered pain sensation in the patient after breast conserving surgery. The pain can be unilateral (usually the shoulder on the affected side) or may involve both shoulders, but is more pronounced on the affected side.

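### Infection is defined by the incision site, which differs between the groups, so a breast or cavity infection may be counted in a control and not in a robotic patient

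*SAP*

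**What the plan says.** Section 5.1.1 lists the adverse events and defines each. Under item (5), infection means organisms that "invade the incision site, and grow and reproduce in it, causing local inflammatory reaction", with or without a systemic reaction. The item does not mention the tumour cavity, the dissected tissue or the remaining breast. Item (1) places bleeding more broadly: "the phenomenon of blood vessel rupture at the surgical site and blood outflow outside the blood vessels". Item (4), on emphysema, covers damaged tissue around the wound as well as the wound itself.

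On where the incisions lie:
- **Robotic group.** The study title is "Single-Port Robot-Assisted Breast-Conserving Surgery via Axillary Approach for Breast Cancer", and section 1 argues that "the surgical approach of SPr approach through axillary incision is more advantageous than that of other approaches".
- **Control group.** Section 1 says that "with traditional surgery, it does leave a permanent scar on the chest". Section 3.5 says only that the operation is "completed with traditional surgery" and gives no incision site.

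The Scenario summary makes safety a main purpose, measured by "the incidence of surgical transfer and the incidence of postoperative complications", and marks the study as not blinded. Section 3.1 lists infection among the postoperative complications and asks for complication rates at 28 and 90 days.

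**The concern.** The position of the incision is a main difference between the two operations. Sections 4.5 and 8.1 say that they differ in approach and otherwise follow essentially the same procedure and principles. An outcome defined by the incision is therefore partly defined by the treatment. If the wording is applied literally, a lower infection count in the robotic group could reflect a wound that lies away from the tumour bed and not a safer operation.

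At stake are the infection comparison and, to a lesser degree, the overall complication rate. Section 4.1 foresees enlarging the sample depending on how this phase goes, so observed rates from a small group may carry weight even without a significant test.

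**Working it through.** **1. Two patients under the literal wording.** The plan gives no infection rate to reproduce, so the first check is to apply item (5) to the same clinical event in each group.

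| | Robotic patient | Control with a breast incision |
|---|---|---|
| Event | Infected tumour cavity, clean wound in the axilla | Infected tumour cavity beneath the incision |
| Incision site involved? | No | Yes, or arguably yes |
| Infection under item (5)? | Not on a literal reading | Yes |
| Infection if item (5) said surgical site, as item (1) does? | Yes | Yes |

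The difference in the third row comes from the wording alone. The right-hand column assumes an incision over or next to the cavity. The background remark about a chest scar suggests this, but section 3.5 does not fix it.

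**2. Weight of one event.** This step needs no assumed infection rate. The robotic group has 20 patients (Scenario summary and section 4.1), so one uncounted infection changes its rate by 1/20 = 5 percentage points. In the control group one event is worth 1/80 = 1.25 points (Scenario summary) or 1/60 = 1.7 points (section 4.1).

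**3. Illustration of a possible size.** Let p be the true infection risk, equal in both groups, and s the share of robotic-group infections that spare the axillary wound and go uncounted. Then:
- recorded robotic rate = p(1 − s)
- recorded control rate = p
- spurious difference = p × s
- expected uncounted infections = 20 × p × s
- chance of at least one uncounted = 1 − (1 − p × s)^20

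Neither p nor s is in the document. I assume p from 2% to 7% and s from 25% to 100%. The upper limit for p is generous, because 7% is the section 1 rate for all complications of open surgery.

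| p | s | Recorded robotic v control | Spurious difference | Expected uncounted in 20 | Chance of at least one uncounted |
|---|---|---|---|---|---|
| 2% | 25% | 1.5% v 2% | 0.5 points | 0.1 | 10% |
| 5% | 50% | 2.5% v 5% | 2.5 points | 0.5 | 40% |
| 7% | 50% | 3.5% v 7% | 3.5 points | 0.7 | 51% |
| 7% | 100% | 0% v 7% | 7 points | 1.4 | 77% |

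The range is 0.5 to 7 points. It is as wide as the assumptions behind it and estimates nothing in this trial. With one definition over the whole field, s = 0 and the spurious difference is zero.

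**4. Effect on a test.** For the all-complication rates quoted in section 1 (7% open, 3.9% robotic), the normal-approximation power of a two-sided 5% test is about 4% with 20 v 80 and about 5% with 20 v 60. The approximation is crude at such counts, but the message is clear: any harm would be to the reported rates and not to a p-value.

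**The case against.** Four counter-arguments carry weight.

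- **The control incision is unknown.** Section 3.5 does not give it, and the first inclusion criterion, written for all subjects, reads "The patient himself has very high requirements for beauty, and requires no scar on the chest". Some controls may therefore have incisions away from the tumour. This stands, and it is why the contrast in step 1 can only be conditional. It does not rescue the definition, which would miss cavity infections in those controls too, so the imbalance would depend on incision placement.
- **Item (5) is descriptive prose in rough English.** Incision site may be meant loosely, for the whole operated area. That is possible. But the item stands under a heading that calls it a definition, the causes it lists concern the wound and its care, and neighbouring items are broader. Two fair readings in an unblinded comparison are themselves the defect.
- **Such infections would still be recorded.** Sections 3.1, 4.5 and 8.1 name infection with no site limit, section 5.2 requires adverse events to be documented, and section 6.2 refers to CRF filling instructions that are not shown. This largely stands: the event need not be lost, and the overall complication rate is less exposed than the infection category. But recording an event does not settle how it is classified, and no section shown says how a cavity infection away from the incision is classed.
- **Infection is not the only complication that can be compared.** Bleeding, flap or nipple-areola necrosis, emphysema and shoulder pain can also occur in both groups. This stands and limits the consequences.

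**Conclusion.** The point holds as a risk of differential counting. The wording of item (5) permits an infection count that depends on the group. The direction, if it occurs, favours the robot. This rests on a literal reading and on at least some controls having an incision over or near the tumour bed.

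A reader might go further in two ways that the document does not support. The first is that the same infection definitely counts in a control and is definitely missed in a robotic patient. The unspecified control incision and the general recording of adverse events rule out that certainty. The second is that the artefact matches the 3.1-point advantage (7% − 3.9%) quoted in section 1. Those rates cover all complications, and no infection rate or split by location is given, so no such match can be shown.

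The one firm figure is that a single uncounted infection among 20 robotic patients moves that group's rate by 5 points.

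**What to change.** In section 5.1.1(5), replace the reference to the incision site with the whole operative field: skin incision, dissection tract, tumour cavity, remaining breast and axilla. State that the definition applies identically in both groups. Add a CRF item for the location of each infection, so that wound and deeper infections can also be shown separately.

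The cost is one sentence and one CRF field. The recorded infection rate may be slightly higher as a result.

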### 5.1.2 Severity

Mild: The discomfort is usually transient and does not affect daily life and

normal activities.

Moderate: discomfort is enough to interfere with daily life and normal activities.

Severe: a serious obstruction to normal activities.

## 5.2 Adverse event management, follow-up, and reporting of serious adverse events

Detailed to the study participants before enrollment, participants were required to truthfully respond to the changes of the condition after intervention treatment, avoid inducing questions, pay close attention to the adverse events, analyze the causes and make a judgment. If adverse events occur during the study, record the time, symptoms, duration, treatment measures and outcome of adverse events in the medical record / case report form, and evaluate the relationship with the study drug; in case of laboratory abnormalities, follow up until the examination results return to normal. The serious adverse events form should be completed and reported to the Ethics Committee and the Clinical Research Management Office within 24 hours.

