shows that Jingfeng ®SP1000 is the first single-port surgical robot to enter the registered clinical trial in China. Jingfeng Medical ® has cooperated with top hospitals and top experts in China to carry out in-depth clinical research and trial of all departments of single-port surgical robot. At present, Jingfeng ®SP1000 has been approved for gynecological indications, and completed registered clinical trials in urology, general surgery, thoracic surgery and other fields, successfully carried out more than 200 clinical operations, demonstrating a wide range of adaptability and excellent performance, bringing new value to scientific research and clinical fields. In addition, professor [name]'s team[29-31]. For the first time, the domestic Jingfeng ®EDGE SP1000 surgical system was used to successfully simulate the key steps of thyroid surgery in the oral thyroid surgery simulator, and realized the high-definition vision and high stability of single-arm robot surgical system, and its smart arm technology, hidden sleeve function and zero pressure anchor point technology are more conducive to ensure the operation safety, this successful practice provides a solid foundation and rich experience for single-port robot breast surgery and related clinical research. However, the safety and effectiveness of the procedure have not been fully verified, and whether the single-port robotic transaxillary breast cancer surgery is more advantageous than the multi-channel operating system (Xi and Si) is not reported. Therefore, this study aims to fill this gap and compare the efficacy and safety of open breast cancer surgery and single-port robot in transaxillary breast cancer surgery through a prospective, single-center phase II clinical cohort study, so as to provide scientific basis for clinical practice and promote the development of minimally invasive breast cancer surgery technology. To provide a theoretical and practical basis for the future application of EDGE SP1000 surgical system in breast cancer surgery. In addition, on this basis, we will systematically establish the technical system and standard for single-port robot breast cancer surgery in our hospital, and lead the formulation of domestic single-port robot-assisted breast cancer surgery standard, which is this the clinical promotion and application of surgery to lay a solid foundation

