## 2. Purpose of Research

To evaluate the safety and feasibility of single-port robot in breast conserving surgery, and compare the advantages and disadvantages of single-port robot and traditional surgery in breast cancer complications, postoperative complications, perioperative recovery effect and safety of breast conserving surgery, so as to choose a more effective and safe surgical method.

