**(3) Standards for suspending or modifying the planned procedure:**

Conversion of SPr-breast conserving surgery to endoscopic or traditional breast conserving surgery is interruption due to technical difficulties or complications during intraoperative anatomical procedures that need to enable an open field conversion for further processing. Surgeons decide whether to switch to endoscopy or open for breast surgery amid concerns about patient safety, technical difficulties, inability to adequately complete robotic surgery or require treatment for related diseases.

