## 5.3 Evaluation of adverse events

The possible association of adverse events and surgical intervention was assessed by the following criteria:

I.Definitely unrelated: adverse events were not associated with the use of surgical intervention. E. g.: No robotic surgery was performed.

II.Probably unrelated: There is no evidence of a causal relationship between the occurrence and surgical intervention. The occurrence of adverse events is more likely to be related to other factors, such as surgical intervention or concomitant diseases. However, the correlation between the two factors cannot be excluded.

III.Possible related: The occurrence of adverse events and surgical intervention have a reasonable chronological order, and the occurrence of adverse events may be caused by surgical intervention. It cannot be excluded from other factors, such as surgical intervention or concomitant diseases. No withdrawal or unclear.

IV.Affirmation: The type of adverse event has been identified as the type of response to surgical intervention and cannot be explained by other reasons (e. g., surgical intervention and concomitant diseases). The timing of the event strongly

suggests causality.

V.Unable to assess: Lack of sufficient information to judge the causality of the event and surgical intervention. The investigator may change the causality assessment she / he does based on the follow-up information and modify the corresponding AE / SAE report.

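### The causality rule for adverse events contradicts itself between sections 5.2 and 5.3 and is circular within 5.3, so relatedness to the robot is not validly defined

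*SAP*

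**What the plan says.** The aim in SAP section 2 is "To evaluate the safety and feasibility of single-port robot in breast conserving surgery". The Scenario summary gives the intervention as "Single-port Robot-assisted breast-conserving surgery for breast cancer", and section 3.5 describes the test arm as "SPr-breast conserving surgery group: using single port robot". No drug is under study.

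Section 5.2 sets out what is written in the medical record or case report form when an adverse event occurs. One item is to "evaluate the relationship with the study drug". Section 5.3 follows with a five-level scale and a different object: "The possible association of adverse events and surgical intervention was assessed by the following criteria". Its illustration for category I, definitely unrelated, is "E. g.: No robotic surgery was performed". Categories II, III and IV each mention other possible explanations, and in all three the examples are surgical intervention and concomitant disease.

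Section 4.5 says that the robotic and open operations differ in the platform used for the approach and are otherwise essentially the same. It says that adverse events will be recorded and discussed, and does not say how relatedness will be summarised.

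**The concern.** A causality rating means something only if the rater knows which exposure is being judged and which other causes compete with it. Here two adjacent sections name different exposures, one of which does not exist in the trial. The scale in 5.3 then puts the same item on both sides of the judgement.

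This matters more than a slip in a peripheral section would. The robot's safety is what the study sets out to judge, and by the account in section 4.5 the platform is the one thing that differs between the groups. For breast surgery the background section concedes that safety and effectiveness are not yet fully verified. The only approval it reports is that the system "has been approved for gynecological indications". A reader of the results will want to know which events were put down to the robot and which to breast-conserving surgery as such. The rule as written cannot answer that.

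**Working it through.** The plan attaches no figure to this point, so the check is a comparison of the text.

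**1. Which exposure is rated?** Section 5.2: a study drug. Section 5.3: surgical intervention. Scenario summary and section 3.5: robotic against traditional surgery. The object in 5.2 matches nothing in the trial. The object in 5.3 fits a surgical trial, but the section does not say whether it means the robotic operation or any breast operation.

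**2. Does either meaning make 5.3 work?**
- If it means the robotic operation, the category I example is consistent, but every control-group event is then definitely unrelated by definition. The Scenario summary plans 80 controls and section 4.1 plans 60. That is 80/100 = 80% or 60/80 = 75% of all patients whose rating is fixed by group membership and not by the event.
- If it means any breast operation, control events can be rated, but the category I example is wrong: an operation took place even though the robot was not used.

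Under neither meaning can related events be compared between the groups with the section as it stands.

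**3. Can the categories be applied?** Take a wound infection (infection is a listed event in 5.1.1) that the investigator believes the operation caused.
- Category IV requires a recognised response to surgical intervention that other reasons do not explain, and gives surgical intervention as one of those reasons. Read literally, no event can qualify.
- Category II applies when other factors, again including surgical intervention, are the likelier cause. The same belief therefore leads to probably unrelated.
- Category III allows a possible relation while not excluding other factors, again including surgical intervention, so it does not discriminate either.
- If the same infection occurs in a control patient, the category I example makes it definitely unrelated.

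**4. Is the robot rated apart from the operation?** No. The only mention of robotic surgery in the scale is the category I example. Nothing asks whether the single-port system contributed to an event in a patient who had the robotic operation.

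**5. Which way would the error run?** This cannot be determined. The category I example forces related events in the control group to zero, which makes the robot look worse. The circular category IV empties the definite category in the robotic group, which makes it look better. Raters will probably improvise between the two.

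**6. What would a valid rating give?** With 20 robotic operations and no robot-related event, the upper exact two-sided 95% limit is 1 − 0.025^(1/20) = 16.8%. If 3 of 20 had one (an assumed count, for illustration), the estimate would be 15% with an exact interval of 3.2% to 37.9%. Neither statement can be made from ratings collected under the present rule.

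**The case against.** The strongest reply is that the drug wording is a template or translation slip that section 5.3 cures. Staff have no drug to rate, 5.3 contains the only scale, and in the test group the surgical intervention is the robotic operation. The first part is fair: nobody is likely to complete a drug rating. But 5.3 does not complete the cure, because its circular alternatives and category I example leave it unusable as written.

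A reader might go further and infer that harm from the robot cannot be reported at all, or that a device fault overcome during the operation would leave no trace. The document does not support that.
- Section 3.1 records intraoperative complications and adverse events.
- Section 5.2 has staff analyse causes, and requires serious events to be reported within 24 hours whatever their attributed cause.
- Section 3.5 defines conversion to include "interruption due to technical difficulties or complications during intraoperative anatomical procedures", and the Scenario summary makes the conversion rate a safety measure.
- Section 7(4) sets up a detailed record of how each intervention was carried out, partly to detect problems. It does not name device faults, but they could be entered there.

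Nor is the lack of a dedicated device-fault field an error in this plan. Such a field commonly sits in a protocol or case report form, and neither is shown.

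It also stands that no planned test or estimate in the SAP uses relatedness. The primary endpoint is margin-negative success, and a comparison of all complications regardless of cause is unaffected.

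**Conclusion.** The point holds as a defect in attribution. Sections 5.2 and 5.3 contradict each other on what an adverse event is judged against, 5.3 is circular in three of its five categories, and its category I example would settle the rating of all control-group events in advance. The robot is never rated apart from the operation.

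The data themselves are not lost: events, serious events and conversions are recorded or reported. What cannot be obtained is a valid count of robot-related events or a between-group comparison of related events. The primary result does not change. The document supports no claim that the feasibility or safety result would be biased in a particular direction, and it gives no device-fault rate from which to size one.

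The conclusion rests on reading section 5.3 as written and on no corrected scale existing in the protocol or case report form. Even if one exists, the SAP text would contradict it. Because this is an operative safety rule in a study of the robot's safety, it should be corrected and is more than clerical.

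**What to change.** - **Section 5.2:** replace the reference to a study drug with two ratings on the adverse event form: relationship to the single-port robotic system (robotic group only) and relationship to the breast operation (both groups).
- **Section 5.3:** apply the scale to each of these named exposures. Delete surgical intervention from the alternative causes in categories II to IV, and delete the category I example.
- **Section 4.5:** report the number of robotic operations with at least one event rated related to the robotic system, out of all robotic operations started, with an exact 95% confidence interval. Counting operations started matters because section 3.3.3 makes conversion an exit criterion. Report events related to the breast operation by group.
- **Events already rated under the current text:** rate them again under the new one.
- **Optional:** a yes/no line for device faults on the intraoperative form in section 6.2(5). This is a low-cost addition, not a correction.

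The cost is a few changed phrases and one extra rating per event in the robotic group, for 20 planned operations. The safety result may look slightly less favourable once events can be attributed to the robot.
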